7.4 Unscheduled or Early Termination Visits

For an unscheduled visit that occurred after the first dose date of IP, the unscheduled visit will be mapped into the closest post-baseline study scheduled visit for the assessment based on the study day of the unscheduled visit, and the target study day of the scheduled visit of the assessment in the protocol. If the unscheduled visit has the equal distance to the 2 study scheduled visits, it will be mapped to the later one.

An unscheduled visit will only be mapped to a study visit within each study period during which it occurs. For example, if an unscheduled visit occurs during the Titration period of the DB Treatment Period I, it should be mapped to the study visit in the Titration period of the DB Treatment Period I.

When there are more than one measurements mapped to the same scheduled visit (including the original measurement taken from the scheduled visit), the measurement taken on the scheduled visit will be used if it is not missing, otherwise the one closest to the target day will be used. If more than one visit has the equal distance to the target day then the later one will be used. If more than one measurement is collected on the same day, use the time or the sequence number to select the latest record. For listings and shift tables, all data points will be included.

Early termination visit will follow the same rule for unscheduled visit as described above.

7.5 Software

SAS[®] software version 9.4 or higher will be used to perform statistical analyses unless otherwise specified.

8 STATISTICAL METHODS OF ANALYSES

8.1 General Principles

All statistical tests will be two-sided and tested at statistical significant level of 0.05. The statistical analyses will be reported using summary tables, figures, and data listings. Continuous variables will be summarized by number of subjects and mean, standard deviation (SD), standard error (SE) median, 25th and 75th quartile, minimum, and maximum values. Categorical variables will be summarized by number and percentage of subjects. All raw data obtained from the CRFs will be included in data listings.

8.2 Subject Accountability

The number and percentage of subjects in each of the study populations (Screened Population, Full Analysis Set, Per Protocol Set and Safety Analysis Set) will be summarized by treatment sequence. Subjects excluded from the analysis sets will be listed.

The number and percentage of subjects who complete each of the two double-blind treatment periods, who complete the OLE Period, and who prematurely discontinue will be presented by treatment sequence. The reasons for premature discontinuation from treatment as recorded on CRFs will be summarized by treatment sequence as well.

8.3 Protocol Deviations

Protocol deviations will be summarized for the Screened Population by treatment sequence and period. Both major and minor protocol deviations will be listed. The determination of major and minor protocol deviations will occur prior to unblinding.

8.4 Demographic and Baseline Characteristics

Summary statistics will be provided by treatment sequence for the Full Analysis Set for the following parameters:

- Age at informed consent
- Gender
- Ethnicity
- Race
- Age at Glut1 DS diagnosis

8.5 Disease Characteristics and Medical History

Summary statistics will be presented for the Full Analysis Set by treatment sequence and overall, for the following parameters:

- Duration of Glut1 DS symptom
- Glut1 DS mutation description
- Glut1 DS symptoms history including whether ongoing
- KD history and reason for KD discontinuation

Medical history will also be summarized by system organ class (SOC) and preferred term (PT) for the Full Analysis Set by treatment sequence.

8.6 Investigational Product Administration

8.6.1 Extent of Exposure

Exposure duration to the investigational product will be summarized by treatment for the Safety Analysis Set for the DB Treatment Period, and the whole study.

8.6.2 Measurement of Treatment Compliance

Dosing compliance for a specified period is defined as the investigational product actually taken by a subject during that period in ml divided by the investigational product expected for the same period in ml multiplied by 100.

Descriptive statistics for dosing compliance will be summarized by treatment sequence and treatment for the Safety Analysis Set for the DB treatment and OLE Period. Number of days with non-missing dose will also be summarized by treatment sequence and treatment.

The percentage of subjects who reach target dose within 2 weeks of titration period will be summarized by treatment for the DB Treatment Period. Time to reach target dose will also be summarized by treatment.

8.6.3 Diet Diary Review

The following measures will be summarized by visit based on the 3-day Diet Diary Review:

- Average Study Drug Calories, as calculated as the average of the 3 entries for study drug
- Average Total Daily Calories

8.7 Prior and Concomitant Medication

Prior medication is defined as any medication started before the date of the first dose of investigational product.

Concomitant medication is defined as any medication taken on or after the date of the first dose of investigational product. A medication started before the date of the first dose of investigational product and also taken after the date of first dose of investigational product will be counted both as a prior and concomitant medication.

Both prior and concomitant medications will be coded by drug name and therapeutic class using World Health Organization (WHO) Drug Dictionary. Prior medications will be summarized by Anatomical Therapeutic Chemical (ATC) code and preferred term by treatment sequence for the Safety Analysis Set. Similarly, concomitant medications will be summarized by treatment sequence for the Safety Analysis Set for the double blind treatment periods and the whole study.

8.8 Efficacy Analyses

Efficacy analyses will be based on the Full Analysis Set, unless otherwise specified.

Section 10.1 Appendix A summarizes the analysis strategy for efficacy endpoints.

For weighted ANCOVA analysis, weight will be calculated by using number of non-missing diary days divided by the planned maintenance period duration (8 weeks). For Wilcoxon rank-sum test, the difference between responses of Treatment Period 1 and Period 2 will be ranked to make the non-parametric comparison between two treatment groups.

8.8.1 Analyses of Primary Efficacy Endpoint

The primary endpoint is the frequency of movement disorder events during the maintenance treatment period. In the event of electronic diary failure, the back-up paper diary might be used during the days with missing data from electronic diary. Combined electronic diary data and paper diary data will be used.

The primary analysis will be performed using a weighted ANCOVA model, with study baseline frequency of movement disorder as a covariate, treatment sequence, treatment group and period as fixed effects, and a random effect for subject within the sequence.

After study unblinding, the normality assumption of ANCOVA model will be examined by using the Wilk-Shapiro test on the residuals from the ANCOVA model (Shapiro et al. 1965). When there is strong evidence suggesting that the normality assumption is not met (p value for Wilk-Shapiro test < 0.05) (Normadiah 2011) (Yap et al. 2011), Wilcoxon rank-sum test will be considered as the primary analysis to assess treatment difference in movement disorder event frequency.

The following sensitivity analyses will be performed.

- To analyze the percent change from study baseline in the frequency of movement disorder during the maintenance period, the primary weighted ANCOVA model will be performed.
- Wilcoxon rank-sum test will be performed to assess treatment difference in movement disorder event frequency.
- The primary weighted ANCOVA based on the frequency of movement disorder events will be performed based on Per Protocol Set.
- In case paper diary is used as back up, sensitivity analysis excluding paper diary will be considered. The primary weighted ANCOVA based on the frequency of movement disorder events will be performed.
- If subjects discontinued during the 2-week titration period or missed one treatment period entirely, impute the movement disorder frequency during the maintenance period using the frequency during the titration period if titration period data is available, otherwise, the study baseline will be used to impute the movement disorder frequency during the maintenance period. Then the ANCOVA model based on the frequency of movement disorder events during maintenance phase will be performed, with study baseline frequency of movement disorder as a covariate, treatment sequence, treatment group and period as fixed effects, and a random effect for subject within the sequence.

Movement disorder frequency during the maintenance period will also be summarized by the subgroup: reporting type of movement disorder diary (caregiver mode or subject mode).

The change from study baseline to maintenance phase in percentage of movement disorder free days will be analyzed using the primary weighted ANCOVA model.

Subgroup analysis by prior KD/Modified Atkins Diet will be conducted for the frequency of movement disorder events using the primary weighted ANCOVA model. If wilcoxon rank-sum test is used as the primary analysis to assess treatment difference in movement disorder event frequency, Wilcoxon rank-sum test will be used to perform the above subgroup analysis. Only point estimate and 95% CI will be presented for the subgroup analysis.

Test Carryover effect

The carryover effect will be tested as the significance of sequence effect. If the carryover effect is non-ignorable (p value < 0.05), analysis including only the first-period data will be considered.

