8.8.2 Analyses of Secondary Efficacy Endpoints

If the primary analysis for the primary efficacy endpoint is statistically significant, then a hierarchically sequential hypothesis testing strategy will be implemented for the selected secondary efficacy endpoints in the following sequence at level 0.05 until first non-rejection:

- Total duration of movement disorder events during maintenance period
- Change from period baseline to treatment week 10 in 12MWT distance
- Patient/caregiver CGI-I score at treatment week 10

The primary analysis for the selected secondary efficacy endpoints are:

- For total duration of movement disorder events during maintenance period, the weighted ANCOVA model will be used with study baseline as a covariate, treatment sequence, treatment group, and period as fixed effects, and a random effect for subject within the sequence.
- For change from period baseline to treatment week 10 in 12MWT distance, the ANCOVA model will be used with period baseline as a covariate, treatment sequence, treatment group, period as fixed effects, and a random effect for subject within the sequence.
- For Patient/caregiver CGI-I score at treatment week 10, the ANCOVA model will be used with Patient/caregiver CGI-S study baseline as a covariate, treatment sequence, treatment group, period as fixed effects, and a random effect for subject within the sequence.
- After study unblinding, the normality assumption of ANCOVA model will be examined by using the Wilk-Shapiro test on the residuals from the ANCOVA model. When there is strong evidence that the assumption is not met (p value for Wilk-Shapiro test < 0.05), Wilcoxon rank-sum test will be considered as the primary analysis to assess treatment difference.

In addition, the following sensitivity analyses for total duration of movement disorder and 12MWT distance will be performed:

- The weighted ANCOVA based on total duration of movement disorder events during maintenance period will be performed based on Per Protocol Set. The mean duration of movement disorder events during maintenance period will be summarized.

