10 APPENDICES

10.1 Appendix A. Efficacy Endpoint Summary Table

Endpoint	Approach	Statistical Method	Analysis Population	Missing Data Imputation (Yes/No)
Primary Endpoint				
Frequency of disabling paroxysmal movement disorder events during maintenance period	P	Weighted ANCOVA	FAS	No
	S	Wilcoxon Rank-Sum Test	FAS	No
		Weighted ANCOVA of the percent change from study baseline in the frequency of movement disorder during the maintenance period	FAS	No
		Weighted ANCOVA with Per Protocol Set	FAS	No
		Weighted ANCOVA (excluding back-up paper diary data)	FAS	No
		Weighted ANCOVA of the change from study baseline to maintenance phase in percentage of movement disorder free days	FAS	No
		ANCOVA	FAS	Yes
		Weighted ANCOVA with subgroups by prior KD/Modified Atkins Diet	FAS	No
		Secondary Endpoints		
Change from period baseline to treatment week 10 in 12MWT distance	P	ANCOVA	FAS	No
	S	ANCOVA	FAS	Yes
		ANCOVA of change from period baseline to treatment week 10 in 6MWT distance and percent predicted 6MWT distance	FAS	No

Endpoint	Approach	Statistical Method	Analysis Population	Missing Data Imputation (Yes/No)
		ANCOVA of change from period baseline to treatment week 10 in percent predicted 6MWT distance	FAS	No
Change from period baseline to treatment week 10 in PROMIS scores	P	ANCOVA	FAS	No
Patient/caregiver CGI-I score at treatment week 10	P	ANCOVA	FAS	No
Total duration of disabling paroxysmal movement disorder events during maintenance period	P	Weighted ANCOVA	FAS	No

Endpoint	Approach	Statistical Method	Analysis Population	Missing Data Imputation (Yes/No)
Change from period baseline to treatment week 10 in CANTAB scores	P	ANCOVA	FAS	No
Other Efficacy Endpoints				
Percent change from study baseline in frequency of disabling paroxysmal movement disorder events over time	P	Descriptive Statistics	FAS	No
Percent change from study baseline in total duration of disabling paroxysmal movement disorder events over time	P	Descriptive Statistics	FAS	No
Physician CGI-S score at treatment week 10	P	ANCOVA	FAS	No
Physician CGI-I score at treatment week 10	P	ANCOVA	FAS	No
Change from study baseline to treatment week 10 in mean daytime activity, mean nighttime activity, and percent time in moderate or higher intensity activity	P	ANCOVA	FAS	No
Change from period baseline to treatment week 10 in COPM performance and satisfaction scores	P	ANCOVA	FAS	No
FAS = Full Analysis Set; P = Primary; S = Sensitivity.				

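### Does the post-unblinding normality check in SAP 8.8.1 and 8.8.2 leave the choice of primary test open?

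*SAP*

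**What the plan says.** SAP 8.8.1 names a weighted ANCOVA as primary: study baseline frequency as covariate; sequence, treatment and period as fixed effects; a random subject effect. It continues: "After study unblinding, the normality assumption of ANCOVA model will be examined by using the Wilk-Shapiro test on the residuals from the ANCOVA model". If the p-value is below 0.05, "Wilcoxon rank-sum test will be considered as the primary analysis to assess treatment difference in movement disorder event frequency". The sensitivity analyses listed in the same section include, without any condition, "Wilcoxon rank-sum test will be performed to assess treatment difference in movement disorder event frequency".

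SAP 8.8.2 repeats the rule for total event duration, 12MWT distance and patient/caregiver CGI-I: "Wilcoxon rank-sum test will be considered as the primary analysis to assess treatment difference". It does so again for PROMIS and CANTAB, which lie outside the hierarchy.

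SAP 8.8 defines the rank test: "the difference between responses of Treatment Period 1 and Period 2 will be ranked to make the non-parametric comparison between two treatment groups". It also states: "Section 10.1 Appendix A summarizes the analysis strategy for efficacy endpoints". In that table the primary endpoint has weighted ANCOVA coded P and "Wilcoxon Rank-Sum Test" coded S (legend: "FAS = Full Analysis Set; P = Primary; S = Sensitivity"). No switch is shown, and the secondary endpoints have no Wilcoxon row.

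The protocol (Synopsis, Efficacy Analysis; Section 7.6.3) already names Wilcoxon as the fallback when normality clearly fails, without giving timing, test or threshold.

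**The concern.** Four features together suggest that the primary test is not settled.

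- **Timing.** The residuals come from a model that contains treatment, so the ANCOVA result exists when the switch is decided. Wilcoxon is run in any case.
- **Wording.** *Considered as the primary analysis* could mean that Wilcoxon becomes primary or that it may become primary. SAP 8.8.1 uses *will be considered* for optional steps too, such as the first-period-only analysis after the carryover test. Appendix A lists only ANCOVA as primary.
- **Residuals.** With a random subject effect, conditional and marginal residuals differ and can lead to opposite switch decisions.
- **Subjects analysed.** The rank test needs both periods, yet Appendix A labels it FAS.

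The primary result opens the 0.05 hierarchy in SAP 8.8.2. A real choice between two p-values after unblinding would therefore inflate the type I error of the main claim.

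**Working it through.** **1. The plan's own figure.** SAP 3.6 gives means of 8 and 4, SD of the difference 7.4, 40 subjects, 15% discontinuation and two-sided 5%. Completers: 40 × 0.85 = 34. Normal approximation: Φ(4 × √34 / 7.4 − 1.96) = Φ(1.19) = 88.3%. With a t-test on 32 df the power is 86.3%. The stated figure of at least 85% reproduces, so the sample size is not in question.

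**2. Is the switch likely to fire?** Take the UX007-period rate as normal with mean 4, and let r be the between-period correlation, assumed to lie between 0 and 0.7.

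- Equal SDs: s = 7.4/√(2(1 − r)), which is 5.23 at r = 0 and 9.55 at r = 0.7. The share below zero, Φ(−4/s), is 22.2% to 33.8%.
- SDs proportional to the mean: s = 7.4/√(5 − 4r), which is 3.31 to 4.99. The share is 11.3% to 21.1%.

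Rates cannot be negative, so skew is plausible and the fallback may well be used.

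**3. The wording, side by side.**

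- SAP 5.5 uses *considered as* to classify: a first-period value does not count as the second period's baseline. The optional uses (paper-diary exclusion and first-period data in 8.8.1) lack the *as*. They speak of doing an analysis, not of giving it a status.
- SAP 8.8.2 says that if one PROMIS or CANTAB domain fails the check, Wilcoxon is primary for all domains. That makes sense only as a mechanical rule.
- SAP 8.8.1 says that if Wilcoxon is the primary test, the prior-diet subgroup analysis uses it too. The switch is thus planned for downstream.
- Appendix A gives the default roles. It omits the switch even for that subgroup row, where the body text states it. It also labels the Per Protocol analysis FAS. It condenses the body text and does not set a rival rule.

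**4. Error rate of the rule.** Simulated trials had 40 randomized subjects, 6 of them with Period 1 only. The weighted mixed ANCOVA used weights of diary days/56 (45-56 days). Wilcoxon used the period differences of the 34 completers. There were 10,000 null trials per case (both means 8; Monte Carlo SE 0.2 points). The documents give no distribution, so all of these are assumed.

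| Assumed data | Switch fires at planned effect | Residual types disagree on switch | Type I error if the better test could be picked |
|---|---|---|---|
| Skewed counts | 94-99% | 2-5% | 6.4-6.9% |
| Milder counts | 51-84% | 8-20% | 5.7-5.8% |
| Zero-censored normal | 33-57% | 18-23% | 5.1-5.6% |
| Normal | 5% | 5% | 5.1% |

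Applied automatically, the rule gives 4.5-5.3% in every case. Each fixed test is also close to nominal: ANCOVA 4.2-5.2%, Wilcoxon 4.5-5.2%.

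A second, simpler simulation (34 completers, equal weights, normal or lognormal-negative-binomial counts, 8,000 null trials) gives 4.6-5.1% with either residual type.

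**5. Does the residual type matter?** In the first simulation it changes the final verdict in 0-2.3% of trials. In the second, the null rejection rate moves by at most 5.12% − 4.94% = 0.18 points. For CGI-I, simulated as rounded 7-point scores, the two types give different switch decisions in 10-29% of trials, but automatic type I error stays at 5.0-5.5%.

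**6. Would one fixed test be better?** Against the automatic switch, fixed ANCOVA changes power by −2.5 to +2.1 points and fixed Wilcoxon by −3.3 to 0. In the second simulation's heaviest-tailed case, fixed ANCOVA loses 99.5% − 92.6% = 6.9 points. There is no uniform gain.

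**The case for a change.** The strongest counter-argument is that the ambiguous sentence would probably be the operative one. If the counts are skewed, the check fails in over 90% of trials in both simulations. At the planned effect ANCOVA and Wilcoxon then disagree at 0.05 often enough to matter: 0-7.9% of trials after a trigger in the first simulation, and 3.2-7.1% of all trials in the second. A reader holding Appendix A could call ANCOVA primary, and a reader holding 8.8.1 could call Wilcoxon primary. Writing *will be* would cost nothing.

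Part of this stands. The residual type is not named, and Appendix A would be clearer with a note on the switch. The rest does not. The inflated error needs an analyst to choose after seeing both results, and no passage permits that. SAP Section 1 and Protocol 7.6.3.1 require departures to be documented in the study report, so such a choice would be visible.

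The timing objection also falls away. Residuals from a model with a treatment term cannot be computed while blinded. Protocol 7.6.3.1 has the SAP final before database lock, and SAP 3.5 puts unblinding after that lock.

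On subjects, ranking a period difference plainly requires both periods (34 of 40 if every discontinuer lacks Period 2). SAP 7.2 uses observed data only, and FAS names the eligible set. The ANCOVA must be fitted to supply the residuals, so it stays available after a switch.

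**Conclusion.** The concern does not call for a change. The SAP fixes a numeric trigger and a named fallback before unblinding. Followed as written, the rule keeps type I error at 4.5-5.3% (4.6-5.1% in the second simulation). The unnamed residual type is a detail that the programming statistician can settle and record before the codes are opened; it alters the verdict in at most 2.3% of simulated trials. Appendix A's silence is a condensed table that yields to the specific text of 8.8.1 and 8.8.2. Replacing the switch with one fixed test is a trade-off of a few power points in either direction, and fixing ANCOVA would remove an alternative named in the protocol.

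This rests on assumed distributions, because the documents give none, and on reading the switch as automatic, which the SAP's own usage supports.

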8.8.2 Analyses of Secondary Efficacy Endpoints

If the primary analysis for the primary efficacy endpoint is statistically significant, then a hierarchically sequential hypothesis testing strategy will be implemented for the selected secondary efficacy endpoints in the following sequence at level 0.05 until first non-rejection:

- Total duration of movement disorder events during maintenance period
- Change from period baseline to treatment week 10 in 12MWT distance
- Patient/caregiver CGI-I score at treatment week 10

The primary analysis for the selected secondary efficacy endpoints are:

- For total duration of movement disorder events during maintenance period, the weighted ANCOVA model will be used with study baseline as a covariate, treatment sequence, treatment group, and period as fixed effects, and a random effect for subject within the sequence.
- For change from period baseline to treatment week 10 in 12MWT distance, the ANCOVA model will be used with period baseline as a covariate, treatment sequence, treatment group, period as fixed effects, and a random effect for subject within the sequence.
- For Patient/caregiver CGI-I score at treatment week 10, the ANCOVA model will be used with Patient/caregiver CGI-S study baseline as a covariate, treatment sequence, treatment group, period as fixed effects, and a random effect for subject within the sequence.
- After study unblinding, the normality assumption of ANCOVA model will be examined by using the Wilk-Shapiro test on the residuals from the ANCOVA model. When there is strong evidence that the assumption is not met (p value for Wilk-Shapiro test < 0.05), Wilcoxon rank-sum test will be considered as the primary analysis to assess treatment difference.

In addition, the following sensitivity analyses for total duration of movement disorder and 12MWT distance will be performed:

- The weighted ANCOVA based on total duration of movement disorder events during maintenance period will be performed based on Per Protocol Set. The mean duration of movement disorder events during maintenance period will be summarized.
- In case there is missing data in 12MWT distance, the following ordered procedure of missing data imputation will be considered: if the subject is missing post-baseline data at treatment week 10, impute the corresponding period baseline. If the subject is missing the second period baseline, impute the study baseline as the period baseline for the second period. If the subject is missing study baseline but has complete second period data, then only count the subjects for the second period

And then the primary ANCOVA model based on the 12MWT distance will be performed.

- Change from period baseline to treatment week 10 in the first 6MWT distance and percent predicted 6MWT distance will be analyzed by the ANCOVA model with period baseline as a covariate, treatment sequence, treatment group, period as fixed effects, and a random effect for subject within the sequence.

For the rest of the secondary endpoints, change from period baseline to treatment week 10 in PROMIS domain scores and change from period baseline to treatment week 10 in CANTAB scores, the primary analysis are:

- ANCOVA model with period baseline as a covariate, treatment sequence, treatment group, period as fixed effects, and a random effect for subject within the sequence will be used.
- After study unblinding, the normality assumption of ANCOVA model will be examined by using the Wilk-Shapiro test on the residuals from the ANCOVA model. When the assumption is not met (p value for Wilk-Shapiro test < 0.05), Wilcoxon rank-sum test will be considered as the primary analysis to assess treatment difference. If any of the domains fails the normality check, the Wilcoxon rank-sum test will be considered as primary analysis for all domains.

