3.6 Sample Size Considerations

The primary efficacy parameter is number of disabling paroxysmal movement disorder events observed during the Maintenance Period of Treatment Periods I and II. Based on the targeted patient population and eligibility criteria, it is estimated that during a 6 week duration, the subjects receiving placebo will have a mean frequency of 8 disabling paroxysmal movement disorders per 4 weeks, while subjects receiving UX007 will have a mean frequency of 4 disabling paroxysmal movement disorders per 4 weeks, and a standard deviation of the difference of 7.4. A total sample size of 40 subjects (20 subjects in each treatment sequence) will have at least 85% power to detect such difference between UX007 and placebo groups at the two-sided 5% significance level. This sample size assumption incorporates a projected discontinuation rate of 15%.

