8.8.3 Analyses of Exploratory Efficacy Endpoints

An ANCOVA model with period baseline as a covariate, treatment sequence, treatment group, period as fixed effects, and a random effect for subject within the sequence, will be used to analyze change from period baseline to treatment week 10 in performance score and change from period baseline to treatment week 10 in satisfaction score as assessed by COPM.

An ANCOVA model with study baseline as a covariate, treatment sequence, treatment group, period as fixed effects, and a random effect for subject within the sequence, will be used to analyze the following other efficacy endpoints:

- Physician CGI-I score at treatment week 10, the Physician CGI-S study baseline will be used as an explanatory variable
- Physician CGI-S score at treatment week 10, the Physician CGI-S period baseline will be used as an explanatory variable
- Change from study baseline to treatment week 10 in mean daytime activity, mean nighttime activity, and percent time in moderate or higher intensity activity as measured by a wrist-worn actigraphy device at select study sites where feasible

Frequency, mean duration and total duration of disabling paroxysmal movement disorder events over time throughout the three-year OLE period will be summarized. Change from

study baseline in percentage of movement disorder free days during the three-year OLE period will also be summarized.

Efficacy Endpoints during the three-year OLE period including 12MWT, Patient/caregiver CGI-I, CANTAB, Physician CGI-I, Physician CGI-S, performance score and satisfaction score as assessed by COPM, PROMIS scores (domain scores) will be summarized and study baseline will be used.

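### A single slope on the period baseline in the 12MWT model (and 6MWT, PROMIS, CANTAB, COPM) costs precision, by an amount that depends on correlations the documents do not give

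*SAP*

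**What the plan says.** - **12MWT.** SAP 8.8.2 analyses change from period baseline to treatment week 10: "the ANCOVA model will be used with period baseline as a covariate, treatment sequence, treatment group, period as fixed effects", plus a random subject effect.
- **Other endpoints.** The two 6MWT distances have the same model. For PROMIS and CANTAB the SAP again specifies an "ANCOVA model with period baseline as a covariate, treatment sequence, treatment group, period as fixed effects", and SAP 8.8.3 does so for COPM: "An ANCOVA model with period baseline as a covariate, treatment sequence, treatment group, period as fixed effects". Physician CGI-S in SAP 8.8.3 also takes its period baseline as explanatory variable.
- **Period baseline.** SAP 5.5 defines it separately for each double-blind period and bars a first-period value from serving as the second baseline. It therefore differs within a subject (Week 0 and Week 12).
- **Protocol baseline.** The synopsis and Protocol 7.6.3.2 use one baseline for change endpoints: the last value on or before the first dose of the first period. That is constant within a subject.
- **Testing order.** SAP 8.8.2 tests total duration, then 12MWT, then patient/caregiver CGI-I, after a significant primary result and until the first non-rejection. PROMIS and CANTAB are outside the sequence; COPM and physician CGI-S are exploratory.
- **Fallback.** If residuals fail the normality check, SAP 8.8 and 8.8.2 switch to a Wilcoxon rank-sum test on the difference between the two periods' responses.

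**The concern.** The covariate carries two different relations. Between subjects, a person's stable walking level cancels from the change score, so change is only weakly related to baseline. Within a subject, a period baseline that is high by chance lowers the change in that period, almost one for one if nothing else links the two visits. The treatment effect is a within-subject contrast, so it needs the within-subject slope. A single slope beside a random subject effect is pulled toward the between-subject slope, because most of the spread in baseline lies between people. The contrast is then adjusted by the wrong amount.

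The stake is precision in a test that has no planned power of its own. The trial is sized for event frequency only. 12MWT is second among the gated secondary endpoints, so an avoidable miss there also closes the CGI-I test.

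**Working it through.** **The plan's own figure.** SAP 3.6 assumes a placebo "mean frequency of 8 disabling paroxysmal movement disorders per 4 weeks", a UX007 "mean frequency of 4 disabling paroxysmal movement disorders per 4 weeks" "and a standard deviation of the difference of 7.4", and 15% discontinuation. Completers: 40 × 0.85 = 34. Noncentrality: 4 / (7.4/√34) = 3.15. Power "at the two-sided 5% significance level" is 88.3% by normal approximation, 86.4% by paired t and 86.3% with n − 2 degrees of freedom. The claim of at least 85% reproduces, but it covers event frequency only. No variance or correlation is stated for 12MWT, 6MWT, PROMIS, CANTAB or COPM, so those below are assumptions.

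**Set-up.** Let B1, Y1, B2, Y2 be the baseline and week 10 values in the two periods, with equal variances. Let r be the correlation between any two visits, and d the extra correlation between baseline and week 10 of the same period. Slopes are for week 10 on baseline; subtract 1 for the change-score model.

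- Within-subject slope (period differences): bw = d / (1 − r).
- Between-subject slope (subject sums): bb = (2r + d) / (1 + r).
- The SAP's single slope b comes from maximum likelihood, minimising ln Vb(b) + ln Vw(b). Here Vb and Vw are the residual variances of the sums and the differences, with Vb at least Vw.
- The treatment SE is proportional to the SD of (Y1 − Y2) − b(B1 − B2). Its ratio to the SE with separate slopes is √[(1 + b² − 2·b·bw) / (1 − bw²)].

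**Example, r = 0.8, d = 0.** bw = 0; bb = 1.6/1.8 = 0.89; fitted b = 0.78. Ratio = √(1 + 0.782²) = √1.61 = 1.27.

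| r | d | bb | bw | b | SE ratio, large sample | SE ratio, simulated, n = 34 |
|---|---|---|---|---|---|---|
| 0.3 | 0 | 0.46 | 0 | 0.26 | 1.03 | not run |
| 0.5 | 0 | 0.67 | 0 | 0.44 | 1.09 | 1.07 |
| 0.7 | 0 | 0.82 | 0 | 0.66 | 1.20 | 1.18 |
| 0.8 | 0 | 0.89 | 0 | 0.78 | 1.27 | 1.25 |
| 0.9 | 0 | 0.95 | 0 | 0.90 | 1.34 | 1.32 |
| 0.7 | 0.10 | 0.88 | 0.33 | 0.79 | 1.11 | 1.10 |
| 0.8 | 0.05 | 0.92 | 0.25 | 0.84 | 1.17 | 1.13 |
| 0.8 | 0.10 | 0.94 | 0.50 | 0.90 | 1.10 | 1.08 |

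The last column is from REML fits, 3,000 simulated trials per case. At r = 0.95 with d = 0 the large-sample ratio reaches 1.38. With correlation decaying over Weeks 0, 10, 12 and 22 it is 1.20-1.35. Over all cases with extra same-period correlation it is 1.05-1.17. Type I error was 4.2-6.2%.

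**In metres.** With assumed between-subject and visit-to-visit SDs, r = between² / (between² + visit²). For 200/60, r = 40,000/43,600 = 0.92 and the simulated ratio was about 1.3. For 100/60 (r = 0.74) it was 1.21; for 150/100 (r = 0.69), 1.15-1.17; for 100/100 (r = 0.5), 1.06-1.10.

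**Power.** If the separate-slope analysis had 80% power, its noncentrality would be 1.96 + 0.84 = 2.80. Dividing by 1.20 gives 2.33 and 65% power; by 1.35, 2.08 and 55%; by 1.09, 2.57 and 73%. In sample-size terms, 1.20² = 1.44 and 1.35² = 1.82 times the subjects.

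**Carryover, if any.** Suppose half of a true effect δ persisted at the Week 12 baseline only. It would enter one sequence, shifting the estimate by b × (δ/2) / 2 = bδ/4. At b = 0.78 that is about 20% of δ. With separate slopes it is bw·δ/4: 0 when d = 0, and about 8% when bw = 0.33.

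**The case against.** The strongest reply is that the model is valid and only the size is in dispute. That largely stands, and it rules out several stronger readings.

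- A reader might take 20-35% as a fact about this trial. The documents supply no variance or correlation from which to derive it. Plausible inputs also give 3-17%, and the range should not be carried unchanged to PROMIS, CANTAB or COPM.
- A reader might infer an invalid test. Simulated type I error stayed near 5%.
- A reader might infer that the crossover's within-subject comparison is lost. It is not: the random subject effect keeps it. With strong same-period correlation the SAP model can even beat an analysis without the period baseline (SE ratio 0.78-0.96 in those cases).
- A reader might infer a carryover bias. The half-effect persistence is hypothetical, and a 2-week washout is planned. What stands is that the single slope would pass on more of any persistence at Week 12.

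Two further replies limit the scope. Under the protocol's study baseline, the covariate is constant within a subject and the conflict of slopes disappears. And the Wilcoxon fallback has no baseline adjustment, so the choice of covariates does not reach it. If it ranks change scores, it keeps the baseline noise in full: b = 1 gives √2, an SE about 41% larger under equal correlation. Neither reply removes the loss under the ANCOVA that the SAP names.

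**Conclusion.** The concern holds as a loss of precision. SAP 8.8.2 and 8.8.3 give a time-varying baseline one slope beside a random subject effect, and in every scenario examined the SE was larger than with separate between- and within-subject slopes.

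Assuming 34 completers and equal variances, the excess is about 20-35% for repeat correlations of about 0.7-0.9 with no extra same-period correlation (18-32% in the simulation at that sample size). It is about 3-17% if correlations are lower or same-period correlation is higher. Any carryover consequence is conditional on an effect persisting at Week 12.

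The practical weight falls on 12MWT, the only affected endpoint in the fixed sequence, and only once the primary endpoint and total duration have succeeded. This is a cheap improvement worth making, not a defect that invalidates the analysis.

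**What to change.** Before unblinding:

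1. Reconcile the SAP's period baseline with the study baseline in the protocol synopsis and 7.6.3.2. If the study baseline is adopted, the rest of this change is not needed.
2. If the period baseline is kept, replace the single covariate in SAP 8.8.2 with two: (a) the subject's mean of the available period baselines, and (b) the period baseline minus that mean, set to 0 when only one period is observed. Leave the other model terms unchanged.
3. Apply this to 12MWT first, then to both 6MWT distances, PROMIS, CANTAB, COPM and physician CGI-S.
4. State which response the Wilcoxon fallback ranks for these endpoints, since step 2 does not affect it.

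Splitting the covariate is safer than dropping it, because dropping it loses precision when same-period correlation is strong. The cost is a short SAP edit and one degree of freedom, with no new data or visits. The gain is small if correlations turn out low.
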